5. STUDY CONDUCT

5.1 Restrictions during the study

1. Fast from at least 10 hours before the planned start of investigational product administration. A moderate amount of water is allowed up to 1 hour prior to investigational product administration and may be resumed 1 hour after administration of the investigational product. A meal can be consumed 4 hours after administration of the investigational product.

Healthy volunteers randomized to either cohort 3a or cohort 4a need only to fast from 4 hours before the planned start of investigational product administration.

2. Eat and drink only the standardized meals and drinks provided (apart from water) during the residential period in the study center.

3. Abstain from consuming any of the following:
 - Alcohol from 72 hours before admission, during the residential period
 - Energy drinks containing taurine or glucuronolactone eg, Red Bull from 72 hours before admission, during the residential period
 - Caffeine-containing drinks during the residential period apart from any provided as part of a standardized meal.
 - Poppy seeds found in speciality bread from time of consent until after the final medical examination
 - Grapefruit, grapefruit juice, Seville oranges, Seville orange marmalade or other products containing grapefruit or Seville oranges from 7 days before admission until after the final medical examination
4. Abstain from nicotine use, smoking and drugs of abuse from the time of informed consent until after the final medical examination
5. Abstain from taking any medication (prescribed or over the counter products), other than paracetamol/acetaminophen and if applicable, hormone replacement therapy, from 2 weeks prior to the first administration of the investigational product until after the final medical examination. However, this should not obviate necessary medical treatment. If any medication is necessary during the residential period, it should be prescribed by the Investigator and the AstraZeneca Clinical Pharmacology Alliance (CPA) Physician should be informed.
6. Healthy volunteers should refrain from strenuous physical activity, which is not within the healthy volunteer's normal daily routine, from 7 days prior to admission to the study center until after the final medical examination.
7. Abstain from blood or plasma donation until 3 months after the final medical examination.
8. Male healthy volunteers should use a condom and spermicide to prevent pregnancy and drug exposure of a partner and refrain from donating sperm or fathering a child from the date of investigational product administration until 3 months after administration with the investigational product

5.2 Subject enrolment, randomization and initiation of investigational product

The Principal Investigator will:

1. Obtain signed informed consent from each potential healthy volunteer before any study specific procedures are performed

2. Assign each potential healthy volunteer a unique enrolment number, beginning with 'E#0001001'
3. Determine the eligibility of each healthy volunteer, see Sections 4.1 and 4.2
4. Assign each eligible healthy volunteer an unique randomization number as described below

If a healthy volunteer withdraws from participation in the study, then his/her enrolment/randomization code cannot be reused.

5.2.1 Procedures for randomization

Healthy volunteers will be enrolled into cohorts sequentially and randomization codes will be assigned sequentially as healthy volunteers become eligible for randomization (ie, the first 12 eligible healthy volunteers will be enrolled into cohort 1 and be randomized sequentially; the next 12 eligible healthy volunteers will be enrolled into cohort 2 and be randomized sequentially and so on). A randomization scheme will be produced by Quintiles using the global randomization system (GRand). The randomization will be done for each cohort using consecutive randomization codes (Volunteer numbers).

Within each cohort except for cohort 3a, healthy volunteers will be randomized in a cross-over fashion. Each healthy volunteer will be randomized to one of these 2 treatment sequences:

1. Platelet apheresis and transfusion in Period 1 → no platelet apheresis and transfusion in Period 2
2. No platelet apheresis and transfusion in Period 1 → platelet apheresis and transfusion in Period 2

The following volunteer numbers will be used for each cohort:

Cohort	Randomization	Condition to run cohort
1	1001 to 1012	Not applicable
2	2001 to 2012	Not applicable
3a	3001 to 3012	If both cohorts 1 & 2 are successful
3b	3001 to 3012	If cohort 1 unsuccessful and cohort 2 is
4a	4001 to 4012	If cohort 3a is successful
4b	4001 to 4012	If cohort 3a is unsuccessful

5.3 Procedures for handling subjects incorrectly randomized

Healthy volunteers who fail to meet the inclusion/exclusion criteria should not, under any circumstances, be enrolled or receive investigational product. There can be no exceptions to this rule.

Where a healthy volunteer, who does not meet the inclusion and/or exclusion criteria, is randomized in error and this is identified before investigational product administration, the

healthy volunteer should be withdrawn from the study. A discussion should occur between the AstraZeneca CPA Physician and the Investigator regarding whether a replacement may be considered.

Where a healthy volunteer, who does not meet the selection criteria, is randomized in error and investigational product administration has been started, or where a healthy volunteer subsequently fails to meet the study criteria post initiation, the Investigator should inform the AstraZeneca CPA Physician immediately. Although investigational product administration should be discontinued, the healthy volunteer should be advised to continue assessments to ensure his/her safety.

The AstraZeneca CPA Physician is to ensure all decisions are appropriately documented.

5.4 Blinding and procedures for unblinding the study (Not applicable)

5.5 Treatments

5.5.1 Identity of investigational product(s)

Please refer to Table 6 for details regarding the investigational product.

Table 6 Identity of the investigational product

Investigational product	Dosage form, strength, and route of administration,	Manufacturer
Ticagrelor	180 mg (2 x 90 mg) tablet, orally	AstraZeneca

The pharmacist at the study center will dispense 180 mg (2 x 90 mg tablets) on Day 1 of each treatment period if enrolled to the ticagrelor cohorts.

Ticagrelor 90 mg will be manufactured in accordance with Good Manufacturing Practice (GMP) and will be purchased commercially by the study center.

5.5.2 Additional study drug

Table 7 Identity of the additional study drugs

Investigational product	Dosage form, strength, and route of administration,	Manufacturer
Acetylsalicylic acid (ASA; aspirin)	81 mg chewable tablet	Bayer
Clopidogrel (PLAVIX®)	300 mg (2 x 300 mg) tablets, orally	Bristol-Myers Squibb/Sanofi Pharmaceutical Partnership

The clopidogrel and ASA will be purchased in the United States by the study center.

The pharmacist at the study center will dispense 600 mg (2 x 300 mg tablets) on Day 1 if enrolled to the clopidogrel cohorts.

A background treatment of ASA (81 mg) will be administered from Day -1 for each treatment period according to the randomization scheme. The ASA administration will occur after the platelet apheresis.

5.5.3 Doses and treatment regimens

Each healthy volunteer will be administered 180 mg ticagrelor or 600 mg clopidogrel, orally, as a single administration on Day 1 of each treatment period, based on the randomization scheme and cohort assignment. The investigational product will be administered after an overnight fast of at least 10 hours and at least 4 hours for cohorts 3a and 4a. For cohort 3a (platelet transfusion at 12 hours) ticagrelor will be administered in the evening. The 180 mg loading dose ticagrelor administrations will be separated by a washout period of at least 14 days.

Background ASA (81 mg once daily) will be administered from either Day -2 (cohort 1) or Day -1 (cohort 2). The ASA administration will commence immediately after the platelet apheresis. The administration and duration of the ASA background treatment will be dependent on the transfusion cohort the healthy volunteer is allocated to ([Table 1](#)).

Each healthy volunteer will have a platelet apheresis either on Day -2 for cohort 1, or on Day -1 for cohort 2, and one autologous apheresis platelet unit transfusion during one of the treatment periods at either 24, 48, or 12 hours based upon the cohort assignment.

5.5.4 Labelling

Labels will be prepared in accordance with GMP and local regulatory guidelines. The labels will fulfil GMP Annex 13 requirements for labelling.

5.5.5 Storage

All investigational products and additional study drug should be kept in a secure place under appropriate storage as specified on the respective labels. Instructions regarding the storage of the platelets will be provided in the Laboratory Manual.

5.6 Concomitant and post-study treatment(s)

If clinically indicated, ticagrelor should be used with caution in the following instances:

- Healthy volunteers with a propensity to bleed (eg, due to recent trauma, recent surgery, active or recent gastrointestinal bleeding or moderate hepatic impairment). The use of ticagrelor is contraindicated in patients with active pathological bleeding and in those with history of intracranial haemorrhage, and severe hepatic impairment

- Healthy volunteers with concomitant administration of medicinal products that may increase the risk of bleeding (eg, non-steroidal anti-inflammatory), oral anticoagulants, and/or fibrinolytics within 24 hours of ticagrelor dosing).
- Since co-administration of ticagrelor with desmopressin did not decrease template bleeding time, desmopressin is unlikely to be effective in managing clinical bleeding events.
- Antifibrinolytic therapy (aminocaproic acid or tranexamic acid) and/or recombinant factor VIIa may augment hemostasis.
- Co-administration of ticagrelor with strong CYP3A4 inhibitors (eg, ketoconazole, clarithromycin, nefazadone, ritonavir, and atazanavir) should be avoided as co-administration may lead to a substantial increase in exposure to ticagrelor.

Other medication, which is considered necessary for the healthy volunteer's safety and well-being, may be given at the discretion of the Investigator and recorded in the appropriate sections of the electronic Case Report Form (eCRF).

5.7 Treatment compliance

The date and time of administration of the investigational product and additional study drugs should be recorded in the appropriate sections of the eCRF.

Treatment compliance will be assured by the supervised administration of the investigational product and additional study drugs by the Investigator or delegate.

5.7.1 Accountability

The investigational product and additional study drugs provided for this study will be used only as directed in the CSP.

The study personnel will account for all investigational product and additional study drugs administered to the healthy volunteers.

The study center personnel will account for all investigational product and additional study drugs received at the study center, unused investigational product and additional study drugs, as well as for the appropriate destruction.

Certificates of delivery and return should be signed.

5.8 Discontinuation of investigational product

Healthy volunteers may be discontinued from investigational product administration in the following situations:

- Healthy volunteer decision. The healthy volunteer is at any time free to discontinue his or her participation in the study, without prejudice to further treatment

- Adverse Event
- Severe non-compliance to the CSP as judged by the Investigator and/or AstraZeneca
- Development of a condition or an acute event (eg, vascular event, MI, or stroke) that necessitates treatment with one or more prohibited medications, or disables the healthy volunteer from following the study procedures
- Safety reasons as judged by the Investigator, AstraZeneca or their delegate
- Incorrect enrolment (ie, the healthy volunteer does not meet the required inclusion/exclusion criteria for the study)
- Pregnancy

Once randomized into the study, all healthy volunteers will be assessed unless they have withdrawn their informed consent for study participation.

Healthy volunteers are at any time free to withdraw from the study (investigational product, additional study drug, and assessments), without prejudice to further treatment (withdrawal of consent). Such healthy volunteers will always be asked about the reason(s) and the presence of any AEs. If possible, they will be seen and assessed by an Investigator. Adverse events will be followed up as applicable.

5.8.1 Procedures for discontinuation of a subject from investigational product administration

A healthy volunteer that decides to discontinue the investigational product administration will always be asked about the reason(s) and the presence of any AEs. If possible, they will be seen and assessed by an Investigator. Adverse events will be followed up (See Sections 6.4.3 and 6.4.4); and all investigational product and additional study drugs should be returned by the healthy volunteer.

If a healthy volunteer is withdrawn from the study, see Section 5.9.

5.9 Withdrawal from study

Healthy volunteers are at any time free to withdraw from the study (investigational product, additional study drugs, and assessments), without prejudice to further treatment (withdrawal of consent). Such healthy volunteers will always be asked about the reason(s) and the presence of any AEs. If possible, they will be seen and assessed by an Investigator. Adverse events will be followed up (See Sections 6.4.3 and 6.4.4).

Withdrawn healthy volunteers will be replaced at the discretion of the Sponsor. Healthy volunteers prematurely withdrawn from the study for any reason may be replaced to ensure that 12 healthy volunteers complete each cohort.

6. COLLECTION OF STUDY VARIABLES

The study assessments are described in the sections below and the timing of these assessments are detailed in the study plan (Table 1).

It is important that blood sampling occurs as close as possible to the scheduled time points. In order to achieve this, other assessments scheduled at the same time point may be initiated prior to the time point. The sequence at a particular time point is:

1. Vital signs measurements
2. Blood sampling for ADP-induced platelet aggregation and VerifyNOW™ P2Y₁₂

6.1 Recording of data

The Investigator will ensure that data are recorded on the eCRFs as specified in the CSP and in accordance with the instructions provided.

The Investigator ensures the accuracy, completeness, and timeliness of the data recorded and of the provision of answers to data queries according to the Clinical Study Agreement (CSA). The Investigator will sign the completed eCRFs. A copy of the completed eCRFs will be archived at the study center.

Procedures for data editing, entry, and handling of the data query process will be described in the Data Management Plan.

6.2 Data collection at enrolment and follow-up

6.2.1 Enrollment procedures

Each healthy volunteer will undergo screening to confirm eligibility. This will consist of the following:

- Obtaining signed and dated written informed consent (and informed consent for pharmacogenetic sample collection) before starting any study-specific procedures
- Review of the inclusion/exclusion criteria with the healthy volunteer
- Recording of demographic data (date of birth, gender, and race)
- A standard recording of medical/surgical history
- A complete physical examination
- Height, weight, and calculation of BMI
- Vital signs (resting supine SBP, DBP, pulse rate, and body temperature)

- Blood sampling for routine clinical chemistry and hematology measurements and a hepatitis B, hepatitis C, HIV screen, FSH, and LH
- Urine sampling for routine urinalysis
- Stool sample for fecal occult blood
- Drugs of abuse and alcohol screen in urine
- Cotinine as per the exclusion criteria
- Pregnancy test (if applicable)
- 12-lead ECG
- AE questioning
- Concomitant medication use

Blood samples for the determination of the CYP2C19 genotype status, only for healthy volunteers to be included in the relevant clopidogrel cohort, will be collected on Days -35 to -30 after they have signed and dated the additional informed consent form.

6.2.2 Follow-up procedures

Follow-up procedures will be performed 7 to 10 days after the last PD sampling. These assessments will include a brief history and physical examination, vital signs, safety laboratory measurements (clinical chemistry, hematology and urinalysis), complete blood count, concomitant medication, and AE questioning.

6.3 Pharmacodynamics

Pharmacodynamic Assessment

- Healthy volunteers will be assigned to receive an autologous platelet transfusion at 24, 48, or 12 hours after the dose of ticagrelor or clopidogrel as illustrated in [Figure 1](#) and noted in [Table 1](#).
- IPA will be determined pre- and posttransfusion by LTA and VerifyNow at the time points noted in [Table 2](#), [Table 3](#), [Table 4](#), and [Table 5](#).

6.4 Safety

The Principal Investigator is responsible for ensuring that all staff involved in the study is familiar with the content of this section.

6.4.1 Definition of adverse events

An AE is the development of an undesirable medical condition or the deterioration of a pre-existing medical condition following or during exposure to a pharmaceutical product, whether or not considered causally related to the product. An undesirable medical condition can be symptoms (eg, nausea, chest pain), signs (eg, tachycardia, enlarged liver) or the abnormal results of an investigation (eg, laboratory findings, ECG). In clinical studies, an AE can include an undesirable medical condition occurring at any time, including screening or washout periods, even if no investigational product and additional study drug have been administered.

The term AE is used to include both serious and non-serious AEs.

6.4.2 Definitions of serious adverse event

A serious adverse event (SAE) is an AE occurring during any study phase (ie, pre-screening, screening, treatment periods, washout, and follow-up), that fulfils one or more of the following criteria:

- Results in death
- Is immediately life-threatening
- Requires in-patient hospitalization or prolongation of existing hospitalization
- Results in persistent or significant disability/incapacity or substantial disruption of the ability to conduct normal life functions
- Is a congenital abnormality or birth defect
- Is an important medical event that may jeopardize the healthy volunteer or may require medical intervention to prevent one of the outcomes listed above

For further guidance on the definition of a SAE, see [Appendix B](#) to the CSP.

6.4.3 Recording of adverse events

Time period for collection of adverse events

Adverse events will be collected from Day -2 up to and including the Follow-up visit.

All SAEs will be recorded from the time of informed consent.

Follow-up of unresolved adverse events

Any AEs that are unresolved at the Follow-up visit in the study are followed up by the Investigator for as long as medically indicated, but without further recording in the eCRF. AstraZeneca retains the right to request additional information for any healthy volunteer with ongoing AE(s)/SAE(s) at the end of the study, if judged necessary.

Variables

The following variables will be collect for each AE;

- AE (verbatim)
- The date and time when the AE started and stopped
- Maximum intensity, rated according to the following scale:
 - Mild (awareness of sign or symptom, but easily tolerated)
 - Moderate (discomfort sufficient to cause interference with normal activities)
 - Severe (incapacitating, with inability to perform normal activities)
- Whether the AE is serious or not
- Investigator causality rating against the investigational product and additional study drugs (yes or no)
- Action taken with regard to the investigational product and additional study drugs
- Whether the AE caused the healthy volunteer's withdrawal from the study (yes or no)
- Outcome

In addition, the following variables will be collected for SAEs:

- Date AE met criteria for SAE
- Date Investigator became aware of the SAE
- AE is serious due to
- Date of hospitalization
- Date of discharge
- Probable cause of death
- Date of death
- Autopsy performed
- Causality assessment in relation to study procedure(s)

- Causality assessment in relation to other medication
- Causality assessment in relation to the investigational product and additional study drugs
- Description of the AE

It is important to distinguish between serious and severe AEs. Severity is a measure of intensity whereas seriousness is defined by the criteria in Section 6.4.2. An AE of severe intensity need not necessarily be considered serious. For example, nausea that persists for several hours may be considered severe nausea, but not an SAE. On the other hand, a stroke that results in only a limited degree of disability may be considered a mild stroke but would be an SAE.

Causality collection

The Investigator will assess causal relationship between investigational product and/or additional study drug and each AE, and answer ‘yes’ or ‘no’ to the question ‘Do you consider that there is a reasonable possibility that the event may have been caused by the investigational product and/or additional study drug?’

For SAEs causal relationship will also be assessed for other medication, study procedures, and additional study drug. Note that for SAEs that could be associated with any study procedure the causal relationship is implied as ‘yes’.

A guide to the interpretation of the causality question is found in [Appendix B](#) to the CSP.

Adverse Events based on signs and symptoms

All AEs spontaneously reported by the healthy volunteer or reported in response to the open question from the study personnel: ‘*Have you/the child had any health problems since the previous visit/you were last asked?*’, or revealed by observation will be collected and recorded in the eCRF. When collecting AEs, the recording of diagnoses is preferred (when possible) to recording a list of signs and symptoms. However, if a diagnosis is known and there are other signs or symptoms that are not generally part of the diagnosis, the diagnosis and each sign or symptom will be recorded separately.

Adverse Events based on examinations and tests

The results from protocol mandated laboratory tests and vital signs will be summarized in the Clinical Study Report (CSR). Deterioration as compared to baseline in protocol-mandated laboratory values, and vital signs should therefore only be reported as AEs if they fulfil any of the SAE criteria or are the reason for discontinuation of treatment with the investigational product.

If deterioration in a laboratory value/vital sign is associated with clinical signs and symptoms, the sign or symptom will be reported as an AE and the associated laboratory result/vital sign will be considered as additional information. Wherever possible the reporting Investigator

uses the clinical, rather than the laboratory term (eg, anemia versus low hemoglobin value). In the absence of clinical signs or symptoms, clinically relevant deteriorations in non-mandated parameters should be reported as AE(s).

Any new or aggravated clinically relevant abnormal medical finding at a physical examination as compared with the baseline assessment will be reported as an AE.

NB. Cases where a healthy volunteer shows an aspartate aminotransferase (AST) **or** alanine aminotransferase (ALT) $\geq 3x$ upper limit of normal (ULN) **or** total bilirubin $\geq 2x$ ULN may need to be reported as SAEs, please refer to [Appendix D](#) 'Actions required in cases of combined increase of Aminotransferase and Total Bilirubin – Hy's Law', for further instructions.

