2.3 Safety objective

To describe the safety and tolerability of ticagrelor administered as a loading dose prior to an autologous platelet transfusion.

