3.1 Overall study design and flow chart

This is an open label, randomized, cross-over study of 180 mg ticagrelor administered in healthy volunteers followed by autologous in vivo platelet transfusion to determine the effects of platelet supplementation on the reversibility of platelet inhibition. The study will be conducted at a single study center in approximately 48 healthy male and female (of non-childbearing potential) volunteers aged 18 to 50 years (inclusive).

The study will consist of 2 treatments each for cohort 1 (platelet transfusion at 24 hours) and cohort 2 (platelet transfusion at 48 hours) (see [Figure 2](#)).

Treatment A: platelet apheresis on Day -2 followed by a ticagrelor 180 mg loading dose on Day 1 for cohort 1; and platelet apheresis on Day -1 followed by a ticagrelor 180 mg loading dose on Day 1 for cohort 2, respectively. Background ASA treatment (81 mg once daily) will commence immediately after platelet apheresis on the relevant day, based on the randomization scheme and treatment group, up to and including the day prior to the platelet transfusion.

Treatment B: ticagrelor 180 mg loading dose on Day 1. Background ASA treatment (81 mg once daily) will commence on the relevant day, based on the randomization scheme and treatment group, up to and including the day prior to the randomized platelet transfusion from Treatment A.

During each treatment period healthy volunteers will receive a loading dose of 180 mg of ticagrelor with background ASA. The healthy volunteers will have platelet apheresis and platelet transfusion performed during 1 of the 2 treatment periods based on the randomization scheme (see [Figure 1](#)).

Cohort 1: will have the platelet transfusion performed 24 hours after receiving the 180 mg ticagrelor loading dose. Healthy volunteers will receive ASA background treatment once on Day -2 immediately after completion of the platelet apheresis, on Day -1, and again on Day 1 when ticagrelor is administered.

Cohort 2: will have the platelet transfusion performed 48 hours after receiving the 180 mg ticagrelor loading dose. Healthy volunteers will receive ASA background treatment once on Day -1 immediately after completion of the platelet apheresis, and again on Day 1 when ticagrelor is administered, as well as once on Day 2.

The cohorts are defined as follows (see [Figure 1](#)):

- Cohort 1 = 24-hour postdose platelet transfusion + ticagrelor
- Cohort 2 = 48-hour postdose platelet transfusion + ticagrelor

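### For non-serious adverse events the protocol records causality against the drugs only, although apheresis plus transfusion is what is randomised

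*Protocol*

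**What the plan says.** Section 6.4.3 lists one causality variable for all AEs, the "Investigator causality rating against the investigational product and additional study drugs (yes or no". The question put to the investigator is "Do you consider that there is a reasonable possibility that the event may have been caused by the investigational product and/or additional study drug". It names no procedure.

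Procedure causality comes in a second list, introduced by "In addition, the following variables will be collected for SAEs", where one item is "Causality assessment in relation to study procedure(s". The text on causality repeats the restriction: "For SAEs causal relationship will also be assessed for other medication, study procedures, and additional study drug".

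Table 7 in Section 5.5.2, titled "Identity of the additional study drugs", lists ASA and clopidogrel and nothing else.

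On design, Section 3.1 states: "During each treatment period healthy volunteers will receive a loading dose of 180 mg of ticagrelor with background ASA". Section 5.2.1 randomises, in every cohort except 3a, the order of a period with apheresis and transfusion and a period with neither. The safety objective in Section 2.3 is "To describe the safety and tolerability of ticagrelor administered as a loading dose prior to an autologous platelet transfusion".

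**The concern.** Treatments A and B give the same drugs. What A adds is an apheresis, an autologous platelet transfusion and the extra blood sampling that follows from the transfusion. The causality item for a non-serious AE asks about the common component and not about the contrast under study. Section 1.4 itself recognises that platelet components carry hazards of their own, with reactions that may appear during transfusion, just after it or some hours later.

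At stake is the safety description. Its objective concerns ticagrelor given ahead of a transfusion, so a reader of the report will want to know which events the investigator ascribed to the drug and which to the procedures. For non-serious AEs the second judgement is never collected. A statistical analysis plan can add a table, but it cannot restore a rating that nobody was asked to give.

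**Working it through.** The protocol states no figure on this point to reproduce. The check sets its sections side by side.

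1. **Which events get a procedure rating?** Under Section 6.4.3, SAEs only. The variable list and the text on causality agree, and no other section extends the rating to non-serious AEs.

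2. **Could the term for additional study drugs cover the procedures?** No. Table 7 limits it to ASA and clopidogrel.

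3. **What separates A from B?** Sections 3.1 and 5.2.1: apheresis plus transfusion. The additional post-transfusion samples are a consequence of the transfusion.

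4. **How would a non-serious procedure reaction be rated under Appendix B?**
   - *Clear case.* The guide lets the investigator answer no when another cause is more likely. That answer is correct, but no listed variable then records that the cause was the apheresis or the transfusion.
   - *Ambiguous case.* The guide says that doubtful events count as a reasonable possibility of drug causation. A plausible time course is one of the factors that can support a yes. It is easily met here: transfusion follows the loading dose by 12, 24 or 48 hours, and in Treatment A the first ASA dose is given straight after apheresis. The default is drug-related.

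5. **What can be recovered from other data?** Section 6.4.3 collects the verbatim term and start and stop times, and prefers a diagnosis to a list of symptoms. Section 12.2.2 summarises AEs by cohort and treatment and reports pre-dose AEs separately. The pre-dose rule isolates some apheresis reactions. It cannot isolate transfusion reactions, which always come after dosing. Its reach for a Period 2 apheresis is unclear, because that apheresis follows the Period 1 dose and Section 12.2.2 places all AEs after the first administration in the tabulations.

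6. **How sharp is the A versus B contrast?** As an illustration only (the protocol names no test for AEs and none is proposed here), take an exact sign test on paired volunteers. If k volunteers have an event in A only and none in B only, the two-sided p-value is 2 × (1/2)^k.
   - k = 5: 2/32 = 0.0625
   - k = 6: 2/64 = 0.031

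   At the 5% level at least 6 of 12 volunteers (50%) in one cohort would have to show the event under A alone, or 6 of 24 (25%) with cohorts 1 and 2 combined. Less frequent reactions would not stand out. Cohort 3a receives Treatment A only, so it has no within-cohort contrast.

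7. **How many volunteers are exposed?** Section 3.1 plans 2 to 4 cohorts of 12: 2 × 12 = 24 to 4 × 12 = 48, each volunteer with one apheresis and one transfusion.

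**The case against.** The case for leaving the protocol as it is has substance, and it rules out several stronger readings that a reader might infer.

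- *That procedure-related AEs cannot be reported at all.* Not supported. A transfusion reaction or a puncture-site haematoma can be entered as a diagnosis and coded, and its onset can be compared with the transfusion time. What is missing is the recorded attribution.
- *That every procedure reaction must be miscoded as drug-related or lose its meaning.* Not supported. Appendix B allows a correct no for a clear case. The pull towards yes concerns ambiguous events.
- *That reported counts of drug-related AEs will be inflated in Treatment A.* Section 12.2.2 names no drug-related AE table, so the effect lies in the recorded rating and in any summary later built on it.
- *That attribution is the only information in cohort 3a.* Term, diagnosis and timing remain, and Treatment B data from cohorts 1 and 2 are available, though not from the same volunteers. Cohort 3a is also conditional on the earlier results.

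Other points stand in part. Serious reactions are already covered: Section 6.4.3 collects procedure causality for SAEs and presumes it wherever a procedure could be involved. An isolated vital-sign change is generally not an AE unless it is serious or stops treatment, so a fall in blood pressure would count mainly when symptomatic. The safety objective names ticagrelor, so a drug rating on every AE does fit it. One may also say that the cross-over estimates the procedure effect without unblinded opinion. That holds at group level, but with 12 volunteers per cohort the contrast is imprecise, and it does not classify single events.

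**Conclusion.** The gap is real and limited. For non-serious AEs the protocol records causality against the drugs and not against the apheresis and transfusion that distinguish the randomised treatments. Clear procedure reactions remain recognisable but carry no procedure attribution; ambiguous ones lean towards drug-related by the protocol's own guide.

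The size is unknown. The protocol gives no rate of procedure reactions, nor the share of AEs expected to be non-serious, so no number of affected events can be stated. The conclusion assumes that the eCRF follows Section 6.4.3 and that no other study document adds the item. The primary pharmacodynamic analysis and the success rules for the cohorts do not depend on it. This is an inexpensive improvement to the safety description; it does not put the trial's main conclusion in doubt.

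**What to change.** In Section 6.4.3, extend the procedure-causality item now reserved for SAEs to every AE, with separate yes/no answers for platelet apheresis and platelet transfusion beside the existing drug rating. Bring the causality question and the Appendix B guide into line, so that an ambiguous event can be marked as possibly related to a procedure as well as to a drug.

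In Section 12.2.2, tabulate drug-related and procedure-related AEs separately by cohort and treatment; for cohort 3a this is Treatment A only.

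The cost is a few more fields on the AE page, slightly longer AE entry and one more table. No visit, sample, procedure or clinical rule changes. The item has to be in place before AEs are collected, since asking for the attribution afterwards would rest on recall and inference.
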